Assessing Success of MTA and Pre-mixed Bioceramic in Mature Teeth With Irreversible Pulpitis With Full Pulpotomy.

(GCP)

NCT05853185

Monday, August 21, 2023

[name]

STUDY PROTOCOL

Operational Definition

Irreversible Pulpitis

Patients with a history of pain score of greater than 4 on visual analogue scale during clinical assessment with lingering of pain for more than 10 seconds on cold stimulus.

Apical Periodontitis

Patients with positive response to tenderness on palpation/percussion and presence of radiographic rarefaction will be diagnosed as positive for apical periodontitis.

Success

Modified Clinical and Radiographic Criteria¹

- Clinical criteria of success
 - No history of spontaneous pain or discomfort except for the first 2 days after treatment
 - No tenderness to palpation or percussion and the tooth is functional.
 - Normal mobility with less than 1mm and probing pocket depth less than 4 mm.
 - Soft tissues around the tooth are normal with no swelling or sinus tract.
- Radiographic criteria of success
 - No pathosis evident on the radiograph such as root resorption, furcal pathosis or new periapical pathosis

Materials and Methods

Study Design

Randomized Controlled Trial (RCT)

Setting

This study will be carried out on patients visiting outpatient clinic of Department of Operative Dentistry, Institute of Dentistry, Department of Operative Dentistry, LUMHS, Jamshoro/Hyderabad

Duration of Study

9 months after approval of study from CPSP

Sampling Technique

Nonprobability convivence sampling

Sample Size

In this trial, based on the results of a previous studies showing a success of 73.8%² with Mineral Trioxide Aggregate and 98.4%¹ for other bioceramics for full pulpotomy procedures, the proportion in population 1 (P1; Mineral Trioxide Aggregate) and the proportion in population 2 (P2 Endosequence Bioceramic Root Repair Material) were determined to be total of 64 with 32 in each group based on Kelsey on Openepi with power of 80% with confidence level of 95.

Inclusion Criteria

- Patients with diagnosis of irreversible pulpitis without apical periodontitis
- Either gender
- Lower Age 10 Years – Upper Age 40 Years

Exclusion Criteria

- Teeth with signs of resorption
- Roots with open apices (Immature Teeth)
- Calcified or blocked canals
- Iatrogenic perforations
- Root fractures
- Non restorable teeth
- Negative response to cold testing and presence of sinus tract or swelling.
- No pulp exposure after caries excavation

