After anesthesia (lidocaine with 1/80,000 epinephrine), complete caries removal, isolation, and pulp exposure, the pulp chamber will be unroofed with a sterile bur, and the pulp from chamber will then be completely removed with a round-end sterile bur on high speed with very low pressure and copious irrigation. After irrigating the chamber with normal saline, a sterile cotton pellet soaked in 5.25% sodium hypochlorite will gently left over the orifices for 10 minutes to achieve hemostasis. After achieving hemostasis, each tooth will randomly be allocated to 1 of 2 parallel arms using a coin toss test performed by a dental assistant who will not be involved in the study. The pulpotomy agent MTA and EndoSequence Bioceramic Root Repair will then be prepared according to the manufacturer's instructions and placed over the orifices with a thickness of approximately 2–3 mm. The cement will then be covered by a layer of light-cured glass ionomer and the remaining cavity will then be restored with

resin-bonded composite. In case of unsuccessful after pulpotomy, teeth will be managed by other pulp therapy techniques.

Data Analysis

Primary outcome for clinical success will be clinical parameters which will be described in binary units, including post-operative pain which will be performed by asking the patient if there is pain either continuous or intermittent, swelling through visual examination, sinus, or fistula through visual examination of the gingiva and tooth mobility by back of mirror to detect mobility in any direction. This assessment will be performed throughout the study at baseline, 6 days, and 6 months. Secondary outcome will be radiographic assessment to detect presence of radiolucency described in binary at baseline, 6 days, and 6 months through periapical radiograph.

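### The items recorded for the primary outcome do not match the protocol's own definition of success, and no rule links the two

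*Combined protocol and SAP*

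**What the plan says.** **Definition.** Operational Definition, under Success, lists the clinical criteria. On pain it requires "No history of spontaneous pain or discomfort except for the first 2 days after treatment". On tenderness and function it requires "No tenderness to palpation or percussion and the tooth is functional". On mobility and probing it requires "Normal mobility with less than 1mm and probing pocket depth less than 4 mm". It also asks for normal soft tissue free of swelling or sinus tract.

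**What is recorded.** The first paragraph of Data Analysis says: "Primary outcome for clinical success will be clinical parameters which will be described in binary units". It names four items and how each is found: pain, by "asking the patient if there is pain either continuous or intermittent"; swelling and sinus or fistula, by looking; and "tooth mobility by back of mirror to detect mobility in any direction". On timing it says "This assessment will be performed throughout the study at baseline, 6 days, and 6 months".

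**What is tested.** The second paragraph of Data Analysis applies chi-square and Fisher's exact tests to the clinical parameters in the two groups. No step there combines the items or returns to the definition of success.

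**Planning rates.** Sample Size relies on earlier studies "showing a success of 73.8%² with Mineral Trioxide Aggregate and 98.4%¹ for other bioceramics", which leads to 32 teeth per group.

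**The concern.** The trial sets out to compare success between two materials. The protocol defines success carefully, but the variables it plans to record and test are worded differently and are never tied back to that definition. Two examiners could follow the two sections faithfully and classify the same tooth differently.

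Some of the loss is permanent. If mobility is recorded as present or absent with no threshold, nobody can later work out which teeth moved by less than 1 mm. If tenderness, function and probing depth are not recorded at follow-up, the defined outcome cannot be rebuilt at all. The reported rates would then describe something other than the protocol's success.

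The trial is also sensitive to small errors. Planned bioceramic success is 98.4%, a failure rate of 1.6%. One misclassified tooth in 32 is 1/32 = 3.1 percentage points, about twice that rate.

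**Working it through.** **Step 1. The two sections side by side.**

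| Criterion | Operational Definition, Success | Data Analysis, primary outcome | Match? |
|---|---|---|---|
| Mobility | Under 1 mm passes | Yes/no, any direction, no threshold stated | No |
| Pain | Spontaneous pain or discomfort; first 2 days exempt | Any continuous or intermittent pain; no exemption or recall period stated | No |
| Tenderness | None to palpation or percussion | Not named | No |
| Function | Tooth functional | Not named | No |
| Probing depth | Under 4 mm | Not named | No |
| Swelling, sinus tract | None | Visual examination | Yes |

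A tooth with detectable movement under 1 mm satisfies the first column and may be marked positive in the second. A tooth tender to percussion, with none of the four named signs, fails the first and passes the second. Errors can therefore run both ways.

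**Step 2. Reproduce the planned sample size.** The inputs from Sample Size are p1 = 0.738, p2 = 0.984, 80% power and 95% confidence; a two-sided test is assumed because sidedness is not stated. The mean is (0.738 + 0.984)/2 = 0.861. Kelsey's formula gives

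n per arm = (1.960 + 0.842)² × 2 × 0.861 × 0.139 / 0.246² = 31.04, rounded up to 32, or 64 in total.

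This matches the plan. It says nothing for or against the mismatch, but it fixes the setting for Step 3.

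**Step 3. Illustrate what one-way errors would cost.** The documents give no misclassification rate, so a fraction e of true successes scored as failures in both arms is assumed, with no false successes. Observed success is p × (1 − e). Power is computed by exact enumeration of all 32 × 32 tables, rejecting at P ≤ 0.05.

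| e (assumed) | MTA | Bioceramic | Difference | Chi-square power | Fisher power |
|---|---|---|---|---|---|
| 0 | 73.8% | 98.4% | 24.6 points | 91% | 76% |
| 2.5% | 72.0% | 95.9% | 24.0 points | 81% | 66% |
| 5% | 70.1% | 93.5% | 23.4 points | 72% | 59% |
| 10% | 66.4% | 88.6% | 22.1 points | 58% | 47% |

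The normal approximation shows the same decline: 82.8% at e = 0, 68.6% at 5% and 56.6% at 10%.

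**Step 4. Where the loss comes from.** From e = 0 to e = 10% the difference shrinks by one tenth. The standard error of the difference, √{[p1(1 − p1) + p2(1 − p2)]/32}, rises from √(0.2091/32) = 0.081 to √(0.3244/32) = 0.101, about a quarter. Most of the power loss is thus added variance, as the bioceramic rate moves away from its ceiling, and less of it is dilution of the difference.

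**The case against.** The strongest reply is that the two sections do different jobs: Operational Definition gives the thresholds, and Data Analysis only describes how each sign is examined. On that reading, the mobility phrase concerns direction, not amount. Since the definition itself treats movement under 1 mm as normal, a yes/no mobility item could mean abnormal mobility only. The list of items is also introduced as inclusive, so the unnamed criteria may be intended.

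This reading is possible, and it rules out the stronger inference a reader might draw: that the recording rules are simply stricter and that teeth meeting the definition are in fact scored as failures. The documents contain no scoring rule that says so. Three further points limit the concern.

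- **The 2-day exemption.** Both follow-up visits fall after day 2, and the pain question is in the present tense. The missing exemption matters only if patients answer for the whole period since treatment, which the wording neither states nor excludes.
- **Provoked pain.** The definition covers discomfort as well as spontaneous pain, so it is not established that a patient with provoked pain would meet it.
- **Planning rates.** One might infer that the recorded items break a match with the criteria behind the 73.8% and 98.4%. The documents do not show which criteria produced either rate, so this cannot be claimed.

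What the reply does not remove is the gap itself. Data Analysis makes the listed items the primary outcome and then tests clinical parameters, without a step that applies the definition. If such a step is intended, it has to be written down.

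**Conclusion.** The point holds as a mismatch without a linking rule. As written, the analysed outcome need not be the defined success. The mobility threshold and the unnamed criteria are the firmest parts; the pain wording is weaker.

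The direction of any net error is not established, because false failures and false successes are both possible. The power figures are therefore not an estimate of what will happen. They assume one-way error, equal in both arms, at rates of 2.5% to 10% that have no source in the documents. At 2.5%, chi-square power of 81% still meets the planned 80%. The Fisher figure of 76% with no misclassification is below 80% for a separate reason, the conservatism of that test. What the figures do show is that, with a planned rate of 98.4% in one arm, even a few misclassified teeth matter.

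This should be corrected before data collection.

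**What to change.** Reconcile the two sections as follows.

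1. Define the primary outcome as one binary variable, clinical success, at each follow-up visit. It requires every clinical criterion in Operational Definition.
2. Record each item in the form the definition uses: mobility under 1 mm (yes/no); spontaneous pain or discomfort since treatment, other than in the first 2 days; tenderness to palpation or percussion; tooth functional; probing depth under 4 mm; swelling or sinus tract.
3. State that the chi-square or Fisher's exact test already planned is applied to that variable. The individual items can still be described by arm.

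The cost is rewording the outcome paragraph and the case form, and repeating at follow-up the palpation, percussion and probing that Data Collection already requires at entry. No extra visit or staff is needed.

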All data will be collected and analyzed in SPSS Version 27. Qualitative data will be presented as frequencies and percentages. Quantitative data will be presented as mean and standard deviation. Chi-square test and Fisher's Exact test will be used for comparisons clinical parameters in two groups. Student's t-test will be used to compare between mean age values in the two groups. Friedman's test will be used to study the changes by time within each group. Kaplan-Meier survival curve will be constructed to calculate the mean survival estimates of the two groups. Comparison between survival times will be performed using Log rank test. The significance level will be set at $P \leq 0.05$.

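### Two tests are named for one binary comparison with no rule for choosing, and the stated 80% power at 32 per group is not reached there by Fisher's test or the usual chi-square/Fisher rule

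*Combined protocol and SAP*

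**What the plan says.** The Data Analysis section names the chi-square test and Fisher's test together: "Exact test will be used for comparisons clinical parameters in two groups". It gives no expected-count rule, does not say whether chi-square is continuity-corrected, and does not say which P-value decides. The threshold is P ≤ 0.05. The same section states "All data will be collected and analyzed in SPSS Version 27".

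The Sample Size section takes 73.8% success for MTA and 98.4% for other bioceramics and arrives at a "total of 64 with 32 in each group based on Kelsey on Openepi with power of 80% with confidence level of 95". It makes no allowance for losses.

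Allocation is described under Data Collection: "each tooth will randomly be allocated to 1 of 2 parallel arms using a coin toss test". There is no blocking, so 32/32 is a target and not a guaranteed split.

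On the outcome, Data Analysis says "Primary outcome for clinical success will be clinical parameters which will be described in binary units" and makes radiographic assessment secondary. The Operational Definition section defines success by "Modified Clinical and Radiographic Criteria".

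**The concern.** About nine failures are expected in total, nearly all in one arm. With so few events, chi-square and Fisher can fall on opposite sides of 0.05 for the same table, and a normal-approximation sample size need not describe either test. Two things are at stake. The reader cannot tell which P-value decides. And the 80% power claimed for 32 per group may not belong to the test that is eventually used.

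**Working it through.** **Inputs.** Success 73.8% and 98.4% (failure 26.2% and 1.6%), 32 per group, 80% power and 95% confidence, all from Sample Size; P ≤ 0.05 from Data Analysis; coin toss from Data Collection. I take the tests as two-sided, which the plan does not state.

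**The plan's own figure.** Kelsey with equal arms: n = (1.960 + 0.842)² × 2 × p̄(1 − p̄) / (p₁ − p₂)². With p̄ = (0.738 + 0.984)/2 = 0.861 and a difference of 0.246:

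n = 7.849 × 2 × 0.861 × 0.139 / 0.0605 = 31.04, rounded up to 32. The sample size arithmetic is right.

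**Why the test matters.** Expected failures at 32/32 are 32 × 0.262 + 32 × 0.016 = 8.4 + 0.5 = 8.9. With equal arms the smallest expected count is half the total failures, so the usual rule (Fisher if any expected count is below 5, otherwise uncorrected chi-square) turns to Fisher at nine failures or fewer. That happens in 60.4% of trials at the planning rates.

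Example, 5 failures vs 0 at 32/32:
- Uncorrected chi-square = 64 × (5 × 32 − 0 × 27)² / (32 × 32 × 5 × 59) = 5.42, P = 0.020.
- Fisher P = 2 × C(32,5)/C(64,5) = 2 × 201,376/7,624,512 = 0.053.
- Boschloo P = 0.033.

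**Exact power and size.** Power is the sum over all tables (x, y) of Bin(x; n₁, 0.262) × Bin(y; n₂, 0.016), counting the tables that the test rejects. Size is the same sum with a common failure rate, maximised over that rate. The coin-toss average weights each split by Bin(n₁; N, 0.5). Boschloo orders tables by the two-sided Fisher P-value.

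| Test | Power, 32/32 | Maximum size, 32/32 | Coin-toss average, 64 | Coin-toss average, 60 (assumed) |
|---|---|---|---|---|
| Fisher | 75.9% | 3.3% | 82.6% | 79.3% |
| Expected-count rule | 77.4% | 6.0% | 83.0% | 79.6% |
| Chi-square, corrected | 75.9% | 3.3% | 76.4% | – |
| Chi-square, uncorrected | 91.3% | 6.0% | 89.4% | – |
| Boschloo | 84.6% | 4.7% | 86.8% | 83.9% |

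The 6.0% sizes are maxima over every possible common rate. For common failure rates of 1% to 26.2%, the rule reaches at most 5.15% and uncorrected chi-square 5.6%. Boschloo's size was at most 4.99% at every split checked.

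**Where the shortfall sits** (MTA/bioceramic, all 64 evaluable):

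| Split | Probability | Fisher | Rule | Boschloo |
|---|---|---|---|---|
| 30/34 | 8.8% | 88.0% | 88.2% | 88.2% |
| 31/33 | 9.6% | 86.0% | 86.2% | 90.0% |
| 32/32 | 9.9% | 75.9% | 77.4% | 84.6% |
| 33/31 | 9.6% | 78.9% | 79.0% | 86.7% |
| 34/30 | 8.8% | 81.6% | 81.6% | 88.5% |

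Splits with power below 80% carry 23% of the probability for Fisher and for the rule, of which 32/32 and 33/31 supply 9.9% + 9.6% = 19.5%. For Boschloo the figure is 4%.

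**Disagreement between the named tests.** Uncorrected chi-square is significant and Fisher is not in 15.4% of trials at 32/32. If the usual rule is followed, the rule and Fisher differ in 1.4% at 32/32 and 0.4% on the coin-toss average.

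**Sensitivity to the bioceramic rate** (assumed values, MTA kept at 73.8%), rule vs Boschloo:
- 95%: 59.9% vs 61.6% at 32/32; 61.9% vs 65.2% on the coin-toss average.
- 92%: 45.4% vs 44.1% at 32/32.
- 90%: 36.4% vs 34.4% at 32/32; 35.8% vs 37.0% on the coin-toss average.

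**The case against.** The strongest reply is that the shortfall reflects the discreteness of particular splits. The coin toss gives exactly 32/32 in only 9.9% of trials, and on the allocation actually planned, with no losses, Fisher and the rule both average above 80%. That stands, and it limits the point to the claim as the Sample Size section words it, which is power at 32 in each group.

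It can also be said that naming the two tests together is commonly read as the expected-count rule, under which the ambiguity changes few verdicts. That also stands. The 15.4% disagreement arises only if uncorrected chi-square could be reported whatever the expected counts. The plan does not exclude this, but it does not propose it either.

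Boschloo is not uniformly better. Its average gain over the rule is 86.8 − 83.0 = 3.8 points at the planning rates, it shrinks as bioceramic success falls, and at 32/32 it reverses at an assumed 92% or 90%. The documents do not show whether SPSS offers the test. So Boschloo is a preference; naming a single test is the necessary part.

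Finally, it is tempting to write the edit as a test of combined clinical and radiographic success at 6 months. The plan does not support that step. Data Analysis makes the clinical parameters primary and radiographic assessment secondary, and nothing says that 73.8% and 98.4% refer to the combined criteria at 6 months.

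**Conclusion.** The point holds in a limited form. The deciding test is not specified, and the stated 80% power at 32 per group is missed there by about 4 points with Fisher (75.9%) and just under 3 points with the usual rule (77.4%). Uncorrected chi-square exceeds 80% but can reach 6.0% size. Of the tests compared, only Boschloo's both exceeds 80% and holds 5% at 32/32.

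A reader might infer that the sample size was miscalculated or that the trial as a whole falls short of 80%. Neither follows. The Kelsey figure is correct, 31/33 is above 80%, and so is the coin-toss average with all 64 evaluable. On that average, Fisher and the rule slip just under 80% at 60 evaluable. The loss of four teeth is my assumption, since the documents give no loss rate.

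All figures rest on a two-sided 5% test, one binary outcome at the planning rates, and independent teeth with one per patient. The plan randomises teeth and does not state a limit of one per patient. The change is worth making, but the trial does not depend on it.

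**What to change.** Before outcome data are seen, state in Data Analysis which single test decides the between-group comparison of the binary primary outcome. Preferred content: Boschloo's exact test, two-sided, tables ordered by the two-sided Fisher P-value and maximised over the common success rate, significant at P ≤ 0.05. The two-sided version must be named, because the version that doubles a one-sided P averages 85.0% instead of 86.8% over coin-toss splits of 64 and differs from the named one in 2.2% of trials.

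Keep n = 64. In Sample Size, restate power for the named test: about 85% at 32/32 and about 87% on the coin-toss average.

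If the investigators prefer to stay in SPSS, write out the expected-count rule and restate its power as about 77% at 32/32 (83% on the coin-toss average). That removes the ambiguity but not the lower power.

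Leave the endpoint unchanged in this edit. The investigators should separately confirm which binary outcome 73.8% and 98.4% describe. The role of the survival comparison ("Comparison between survival times will be performed using Log rank test") is also left open here.

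Cost: one or two sentences and no more patients. The test may have to be run outside SPSS. The average gain over the rule is about 4 points, depends on the planning rates, and can reverse at 32/32 if bioceramic success is nearer 90%.

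### With follow-up only at 6 days and 6 months and no rule for dating failures, the planned Kaplan-Meier mean survival gives little or no weight to failures found at 6 months

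*Combined protocol and SAP*

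**What the plan says.** All of the analysis text is in the Data Analysis section of the combined protocol and SAP.

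- **Outcome data.** "Primary outcome for clinical success will be clinical parameters which will be described in binary units". On timing: "This assessment will be performed throughout the study at baseline, 6 days, and 6 months". The radiographic outcome follows the same schedule: "Secondary outcome will be radiographic assessment to detect presence of radiolucency described in binary at baseline, 6 days, and 6 months through periapical radiograph". Each tooth therefore has two scheduled yes/no readings after treatment, and no date of onset.
- **Survival analysis.** "Kaplan-Meier survival curve will be constructed to calculate the mean survival estimates of the two groups", followed by "Comparison between survival times will be performed using Log rank test". Chi-square and Fisher's exact tests are also planned for the clinical parameters.
- **Failed teeth.** Data Collection says: "In case of unsuccessful after pulpotomy, teeth will be managed by other pulp therapy techniques". No event date or censoring rule is attached to this.
- **Success.** The Operational Definition lists clinical criteria, such as "No tenderness to palpation or percussion and the tooth is functional", and a radiographic criterion. The survival analysis is not tied to either.
- **Sample Size.** The trial is sized on two success proportions, 73.8% and 98.4%, with 32 teeth per arm.

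**The concern.** A Kaplan-Meier mean is the area under the survival curve up to the last observed time. A failure lowers it only through the time remaining after the failure is dated. Here nearly all follow-up lies between two visits, and the second visit is the end of the curve. A failure dated at that visit has no time left after it, so it takes nothing off the mean.

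The mean is the only survival estimate the plan names, and no risk difference or confidence interval is planned beside it. A report could therefore show equal mean survival for two materials whose 6-month success differs by about as much as the trial was sized to find. Because no dating rule is written down, the choice could also be made after the data are seen, and that choice changes the answer.

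**Working it through.** **Inputs from the document.** Success 73.8% (MTA) and 98.4% (bioceramic), 80% power, 95% confidence, 32 per arm (Sample Size); visits at 6 days and 6 months (Data Analysis).

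**Assumptions.** 6 months = day 183; no dropout; planning failure rates of 26.2% and 1.6% of 32 (8.4 and 0.5 teeth) taken as 8 and 1 failures; two-sided alpha 0.05.

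**1. The plan's own figure.** Kelsey formula, with mean proportion (0.738 + 0.984)/2 = 0.861 and difference 0.246:

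n = (1.96 + 0.84)² × 0.861 × 0.139 × 2 / 0.246² = 31.04 (unrounded z values), so 32 per arm and 64 in total. The stated sample size reproduces.

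**2. Kaplan-Meier mean with failures dated at the scheduled visit.** The curve is 1 up to day 6 and S(6) from day 6 to day 183, so

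mean = 6 + (183 − 6) × S(6) = 6 + 177 × S(6).

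Survival at 6 months does not appear. With d failures found at day 6, S(6) = 1 − d/32:

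| d | Mean (days) |
|---|---|
| 0 | 183.0 |
| 1 | 177.5 |
| 2 | 171.9 |
| 4 | 160.9 |
| 8 | 138.75 |

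The zero weight does not depend on the assumed rates: 31 failures v 0, all found at 6 months, also gives 183.0 v 183.0.

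**3. Eight MTA failures v one bioceramic failure, by the visit at which they are found.**

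| Timing | MTA | Bioceramic | Difference (bioceramic − MTA) |
|---|---|---|---|
| All nine at 6 months | 183.0 | 183.0 | 0 |
| 2 MTA at day 6, rest at 6 months | 171.9 | 183.0 | 11.1 |
| 4 MTA at day 6, rest at 6 months | 160.9 | 183.0 | 22.1 |
| All nine at day 6 | 138.75 | 177.5 | 38.7 |
| 8 MTA at day 6, bioceramic failure at 6 months | 138.75 | 183.0 | 44.25 |
| 8 MTA at 6 months, bioceramic failure at day 6 | 183.0 | 177.5 | −5.5 |

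In every row 6-month success is 24/32 = 75.0% v 31/32 = 96.9%, a difference of 21.9 points (Newcombe 95% CI 4.6 to 39.2).

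**4. Actual attendance dates instead of nominal ones.** All failures found at 6 months, attendance uniform in whole days around day 183, mean taken to each arm's last visit, 8,000 simulations:

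| Spread of visits | Average difference (days) | 2.5th to 97.5th percentile |
|---|---|---|
| ±7 days | 2.1 | 0.8 to 3.4 |
| ±14 days | 4.3 | 1.5 to 7.1 |
| ±30 days | 9.3 | 3.2 to 15.0 |

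A common cut-off for both arms gives 2.1, 4.2 and 8.9. The difference grows with the scatter of appointments while the 6-month result stays the same.

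**5. Midpoint dating, for comparison.** If failures found at 6 months are dated at the midpoint, (6 + 183)/2 = day 94.5, each loses 183 − 94.5 = 88.5 days. The difference is then (8 − 1)/32 × 88.5 = 19.4 days (160.9 v 180.2).

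**6. The tests.** With all nine failures tied at 6 months, 9 × 32/64 = 4.5 are expected in the MTA arm, with variance 9 × 0.5 × 0.5 × 55/63 = 1.964. Log-rank chi-square = (8 − 4.5)²/1.964 = 6.24, P = 0.013. Over the other nominal-visit timings the log-rank P runs from 0.0116 to 0.0157. Pearson chi-square P = 0.012 and Fisher P = 0.026. The tests give 6-month failures full weight.

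**The case against.** The strongest reply is that the mean is descriptive. The arms are compared by the log-rank, chi-square and Fisher tests, all of which count 6-month failures. The curve and the planned percentages would show 75% v 97% whatever the mean says. This stands as a limit on the consequence: the risk is a misleading published estimate, not a wrong test result.

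Second, the exact zero requires dating at the nominal visit, which the plan does not state. A tooth retreated between visits might carry its own date and so get ordinary weight. That is also true. But no rule says such dates will be recorded or used, and failures first found at the 6-month visit, for example on the radiograph, would still get little or no weight.

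Third, the reversal needs a particular pattern: all eight failures in the worse arm found at 6 months and the single failure in the better arm at day 6. It shows what the mean can do and is not a forecast.

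Fourth, midpoint dating or an interval-censored method would restore weight, so dropping the mean is not the only remedy. This is fair. With only two visits, however, such a mean would rest largely on the dating convention, whereas the proportion at 6 months needs none.

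**Conclusion.** The concern holds and should be acted on. Applied to the only times the visit schedule supplies, the planned mean gives no weight to failures found at 6 months, or a small weight set by attendance scatter. For the same 21.9-point difference in 6-month success, it can show 0 days, a 5.5-day reversal or a 44-day advantage, depending on the visit at which failures are found. The trial is sized on 24.6 points (98.4 − 73.8).

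The zero weight follows from the formula under nominal-visit dating. The sizes rest on 8 v 1 failures in 32 per arm, day 183 for 6 months, no dropout and, for attendance dates, the assumed spreads. Taking 6 months as 180 days gives the same pattern. The defect is confined to the mean survival estimate.

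**What to change.** In Data Analysis, replace the Kaplan-Meier mean with text such as: *The two materials will be compared on the proportion of teeth meeting the Operational Definition of success at 6 months, reported as a difference with its 95% confidence interval; a tooth found unsuccessful before then is counted as not successful.* This also matches the analysis to the proportions in Sample Size ("the proportion in population 1 (P1; Mineral Trioxide Aggregate) and the proportion in population 2").

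The same text should say whether success here includes the radiographic criterion, because the Operational Definition lists it under success while Data Analysis makes radiographic assessment secondary. It should also say how a tooth with no 6-month visit is counted.

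If the Kaplan-Meier curve and log-rank test are kept, define the event as failure of the Operational Definition criteria. State the time origin, how a failure found at or between visits is dated (including a tooth retreated between visits), and when a tooth is censored. Do not report the mean.

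The cost is wording only, with no new visits or data. The sponsor gives up the mean survival figure.
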